2.2 Data Conventions

Statistics will typically include sample size (N), mean, standard deviation (SD), minimum (Min), and maximum (Max) as appropriate for continuous variables. For categorical data, the frequency and proportion will be computed.

2.3 Randomization

Subjects will not be randomized in this study.

3. Accountability/Demographics

3.1 Enrollment

The number of enrolled subjects will be tabulated by site and by IOL model implanted for first and second eyes. Results will also be reported by low and high cylinder IOL subgroups.

3.2 Accountability

The frequency and proportion of subjects with six month data will be provided for toric and control subjects. For those subjects that did not have data available at the six month visit the reasons for the missing visit will be summarized for toric and control subjects.

3.3 Demographics/Preoperative/Operative Parameters

Subject demographic data including age, sex, race, ethnicity and eye color will be presented for toric and control subjects. Age will be classified by less than 60, 60 to 69, 70 to 79, and equal to or older than 80 years old. In addition, age will be summarized with descriptive statistics. The frequency distributions of sex, race, ethnicity and iris color will also be tabulated.

The frequency and proportion of operative complications and additional operative procedures will be reported for first and second eyes for toric and control subjects.

4. Postoperative Analyses – Key Endpoints

4.1 Visual Distortions – Primary Endpoint

The primary endpoint is the rate of severe visual distortions defined as the proportion of subjects who report a severe visual distortion under overall circumstances at 6 months for any of the 5 defined visual distortion items listed in section 1.0. The frequency and proportion of bilateral subjects with severe visual distortions will be reported along with the two-sided 90% confidence interval at the 6 month visit

A non-inferiority test will be performed to compare the proportion of subjects with severe visual distortions between pooled toric lens models and all control subjects using a non-inferiority margin of 0.10. The null and alternative hypotheses are:

H₀: Toric IOL subjects will have a severe visual distortion rate greater than or equal to 10% of that for ZCB00 subjects.

```
pToric – pZCB00 ≥0.10 (p=proportion with severe visual distortions)
```

H₁: Toric IOL subjects will not have a severe visual distortion rate greater than or equal to 10% of that for ZCB00 subjects

pToric – pZCB00 < 0.10 (p=proportion with severe visual distortions)

The results will be evaluated by examining the upper limit of the two-sided 90% confidence interval of the difference between the two IOL groups (toric minus control) to see if it is greater than or equal to 0.10.

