**2.0 BACKGROUND AND PURPOSE OF STUDY**

It is estimated that 35% of cataract patients have  $\geq 1.00$  diopter of corneal astigmatism^1 with 15%-20% having  $\geq 1.5$  D of corneal astigmatism. Although there are various modalities to reduce the amount of astigmatism during cataract surgery (e.g., limbal relaxing incisions, etc.), toric IOLs are now commonly used for correction of aphakia and pre-existing ocular astigmatism. On April 15, 2013, Abbott Medical Optics (AMO) received USA FDA approval (P980040/S039) for the TECNIS 1-Piece Toric IOL, Models ZCT150, ZCT225, ZCT300 and ZCT400 for the visual correction of aphakia and pre-existing corneal astigmatism of one diopter or greater.

In the IDE registration trial of the TECNIS 1-Piece Toric IOL (G090251), rotational stability was demonstrated and there were minimal subject complaints of visual distortions; however, there is the potential, particularly in the case of toric IOLs that correct for higher amounts of corneal astigmatism, that patients may experience spatial distortions related to axis misalignment, e.g., whether objects appear tilted or misshapen, etc. As a condition of approval, this post-approval study will be conducted to

evaluate visual distortions of the TECNIS Toric 1-Piece IOLs with  $\geq 2.00$  D of cylinder correction at the corneal plane (Models ZCT300 and ZCT400) and to ensure the continued safety of the approved devices.

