## 20.2 PRIMARY ENDPOINT ANALYSIS

The primary endpoint is the rate of severe visual distortions (under overall circumstances) as measured by the 5 defined visual distortion items at 6 months postoperative. The frequency and proportion of bilateral subjects with severe visual distortions will be presented for toric IOL and control IOL subjects. Any subject with missing data for visual distortion symptoms at the 6-month visit will have the last reported value carried forward, if the subject had an earlier visit. Results for severe visual distortions will be evaluated using a non-inferiority approach with a non-inferiority margin of 10%. The upper limit of the 90% confidence interval of the difference in severe visual distortion rates (toric minus control) will be used to evaluate this endpoint.

The null hypothesis,  $H_0$ , is:  $p_{\text{Toric}} - p_{\text{Control}} \geq 0.10$

The alternate hypothesis,  $H_1$ , is:  $p_{\text{Toric}} - p_{\text{Control}} < 0.10$

With  $p$ =proportion reporting severe visual distortions

A logistic regression analysis for severe visual distortions will be performed with age, sex, race, and cylinder subgroup as well as age by IOL group and sex by IOL group as covariates to evaluate the influence of these variables.

To evaluate if toric IOL axis misalignment relative to keratometry are associated with severe visual distortions, descriptive statistics for IOL axis misalignment will be reported for toric subjects with and without severe visual distortions. In this study, axis misalignment is defined as the difference between the toric IOL axis marker location from the slit-lamp evaluation and the steep meridian from the postoperative keratometry measurement. This measurement is intended to evaluate toric IOL misalignment as a possible reason for severe visual distortions experienced by a subject at a specific postoperative time point. This axis misalignment measurement is not a measure of toric IOL rotational stability, but a measure of toric IOL alignment relative to post-surgical keratometry steep meridian, as it is known that cataract surgery can induce changes in the cornea.

The frequency and proportion for the rate of severe visual distortions will also be presented for those in the low- and high-cylinder subgroups for toric and control subjects.

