## 20.6 SAMPLE SIZE

A sample size of a minimum of 396 enrolled subjects to achieve bilateral implantation of approximately 294 subjects: 169 TECNIS Toric ZCT300 and ZCT400 and 125 control subjects is reflective of the number of subjects enrolled on the date of this protocol revision (3.0).

A two-group large-sample normal approximately test of proportions with a one-sided 0.05 significance level using only 37 evaluable toric subjects and 27 evaluable control subjects will have a greater than 90% power to detect a rate of severe visual distortions for toric subjects as being 10 percentage points or greater than that for control subjects. This assumes severe visual distortion rates of 1% for both the toric and control subjects. Therefore, the sample size proposed for a minimum of 396 enrolled subjects, assuming a 10% drop out rate for a minimum of 152 toric and 112 control subjects available for evaluation at 6 months, is sufficient to demonstrate non-inferiority in the rate of severe visual distortions (the primary endpoint of this study) between the two study groups in a larger population in clinical practice and thereby demonstrate the continued safety of the toric IOLs.

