4.2 Other Visual Distortion Endpoints Related to Severe Visual Distortions

In addition to the above information related to the primary endpoint analysis, other analyses will also be performed for severe visual distortion rates (based on the 5 defined items) and will include the frequency and proportion with severe visual distortions. Severe visual distortion data for the overall circumstance will be reported for the low (ZCT300) and high cylinder (ZCT400) subgroups for bilateral subjects to evaluate if there is a trend of increasing severity for the higher cylinder IOL group. The severe visual distortion rate will also be reported by IOL group for all subjects (bilateral plus those implanted in one eye (with a cataract, phakic or having another IOL in the fellow eye). In addition, an analysis including all subjects using imputed data for subjects with no questionnaire data available at any visit will also be reported.

Additional analyses including covariates will also be performed for bilateral subjects. A logistic regression model with overall severe visual distortion rates as the dependent variable and IOL group, age, gender, race, cylinder power (low- vs high-cylinder subgroups) and the interaction of age with IOL group and gender with IOL group as independent variables will be performed to further evaluate the influence of these variables on severe visual distortions. If covariates are shown to be important then additional analyses will be provided for those covariates. Results for severe visual

distortions will also be reported by study site for each IOL group. Although there are a large number of sites, any unusual patterns will be noted (i.e. all severe visual distortions at 1 or 2 sites) and further analyses performed to address any site issues.

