With 200 toric (ZCT) subjects and 150 control (ZCB00) subjects, this study has over 90% power to evaluate the rate of severe visual distortions for toric subjects as being no more than 10 percent higher than control subjects. This assumes use of one side of a two-sided 90% confidence interval and severe visual distortion rates of 0.02 for toric and control subjects.

With approximately 70 subjects in the higher cylinder toric subgroup (those with a ZCT400 IOL in one or both eyes) the precision of the one-sided upper confidence limit for the proportion of those with severe visual distortions is approximately 0.05 to 0.06 assuming a rate for severe visual distortions of 0.02.

REFERENCES

- 1. Little, R.and Rubin, D. Statistical Analysis with Missing Data, John Wiley & Sons, Inc. New York, Second Edition, (2002)
- 2. SAS Institute. The MI and MIanalyze Procedures. SAS/STAT 9.2 User Guide. Cary, N.C.

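### The only test pools ZCT300 with ZCT400, so a pass does not bound ZCT400, and no listed output gives the ZCT400 upper limit that SAP 7 uses to justify the subgroup

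*SAP*

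**What the plan says.** SAP 4.1 specifies a single confirmatory test, which is to "compare the proportion of subjects with severe visual distortions between pooled toric lens models and all control subjects using a non-inferiority margin of 0.10", judged by the upper limit of a two-sided 90% interval. Protocol 20.2 gives the same margin and confidence level. Neither document names the interval method.

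The plan does look at the two toric models separately. Protocol 20.2 states: "The frequency and proportion for the rate of severe visual distortions will also be presented for those in the low- and high-cylinder subgroups". Protocol 20.1 and SAP 2.1 place each control in the low- or high-cylinder group according to the toric lens that the subject would have needed, and count subjects with one eye of each kind as high-cylinder. SAP 4.2 says that its further analyses "will include the frequency and proportion with severe visual distortions" and that the subgroup figures are there to look for a trend with cylinder. In SAP Appendix I the cylinder-subgroup row lists number and percent; the 90% interval appears only in the row for the primary bilateral analysis.

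SAP 7 sizes the higher-cylinder subgroup by a different quantity. With about 70 ZCT400 subjects and a 2% rate, "the precision of the one-sided upper confidence limit for the proportion of those with severe visual distortions is approximately 0.05 to 0.06". Protocol 8.0 now plans 51 ZCT400 subjects out of 169 toric subjects.

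**The concern.** Protocol 2.0 says that spatial distortion from axis misalignment is a possibility "particularly in the case of toric IOLs that correct for higher amounts of corneal astigmatism", and the clinical hypothesis in Protocol 5.0 names both models. The stronger toric lens is therefore where an excess is most plausible, yet it supplies only about three in ten of the toric subjects tested. An excess confined to ZCT400 reaches the pooled difference at 30% of its size.

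The study could thus meet its success criterion while ZCT400 exceeds control by more than the study's own 10-point margin. The planned subgroup table would then carry percentages without limits. An observed 0% or 2% in about 46 subjects looks reassuring, but it does not show how high the true rate could be. SAP 7 evidently meant that question to be answered, and the listed outputs do not answer it.

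**Working it through.** **Inputs.** Evaluable subjects: 152 toric and 112 control (Protocol 20.6). ZCT400: 51 × 0.9 = 45.9, about 46, leaving 152 − 46 = 106 for ZCT300. Margin 0.10, one-sided 0.05. Base rate 1% (Protocol 20.6) or 2% (SAP 7). Assumption: ZCT300 has the same true rate as control, unless stated otherwise.

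**The plan's own figures.**
- Protocol 20.6 says that the test "using only 37 evaluable toric subjects and 27 evaluable control subjects will have a greater than 90% power". The unpooled normal approximation is Φ(0.10/SE − 1.645), with SE = √[0.01 × 0.99 × (1/37 + 1/27)] = 0.0252. It gives Φ(2.33) = 0.99, which agrees.
- SAP 7, 200 against 150 at 2%: the same formula gives more than 0.999, which agrees with its stated power of over 90%.
- SAP 7, ZCT400 limit at n = 70: 0.02 + 1.645 × √(0.02 × 0.98/70) = 0.048. The exact (Clopper-Pearson) limit with 1 event in 70 is 0.066. The stated 0.05 to 0.06 is plausible for 70 subjects.

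**Dilution.** A ZCT400 excess of 10 points gives a pooled excess of 10 × 46/152 = 3.0 points; 14 points gives 4.2. With ZCT300 and control at 1%, the pooled excess reaches 10 points only when the ZCT400 rate is (0.11 × 152 − 0.01 × 106)/46 = 15.66/46 = 34%.

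**Pass probability of the pooled test.** This is an exact enumeration: toric count = Bin(106, p300) + Bin(46, p400), control count = Bin(112, pC). The test passes if the upper 90% limit is below 0.10.

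| Scenario | ZCT400 excess | Score (Farrington-Manning) | Wald |
|---|---|---|---|
| Base 1%, ZCT300 = control | 10 points | 0.955 | 0.968 |
| Base 1%, ZCT300 = control | 14 points | 0.828 | 0.862 |
| Base 2%, ZCT300 = control | 10 points | 0.911 | 0.921 |
| Base 2%, ZCT300 = control | 14 points | 0.762 | 0.776 |
| Base 1%, ZCT300 2 points above control | 10 points | 0.795 | 0.830 |
| Base 1%, ZCT300 2 points above control | 14 points | 0.580 | 0.623 |

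**An illustration by hand.** Take 10 severe reports in 152 toric subjects and 1 in 112 controls. The difference is 0.0658 − 0.0089 = 0.0569. The Wald SE is √(0.0658 × 0.9342/152 + 0.0089 × 0.9911/112) = 0.0220, so the upper limit is 0.0569 + 1.645 × 0.0220 = 0.093 and the test passes. It would pass even if all 10 reports came from the ZCT400 subjects, a rate of 10/46 = 22%.

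**What a ZCT400 limit would show.** Exact one-sided 95% upper limits at n = 46 are 6.3% with 0 events (1 − 0.05^(1/46)), 9.9% with 1 and 13.1% with 2. The normal formula at a 2% rate gives 0.02 + 1.645 × √(0.02 × 0.98/46) = 0.054. Moving from 70 to 46 subjects therefore changes the normal figure little (0.048 to 0.054), but it raises the exact limit with one event from 6.6% to 9.9%.

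**A stratum interval.** Assume 34 high-cylinder controls (30% of 112 = 33.6). With 46 ZCT400 subjects, a score interval for the difference excludes 10 points with probability 0.94 at true rates of 1% and 0.85 at 2%. At a true 10-point excess over a 1% base it excludes 10 points 5.4% of the time, against 11% with Wald.

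**The case against.** The strongest reply is that pooling is the declared design. Protocol 6.0 defines success for the toric group as a whole, and 20.6 speaks of the two study groups. The subgroup results are plainly descriptive. That stands: the pooled test is valid for its pooled hypothesis, and these documents do not oblige the sponsor to make a separate confirmatory claim for ZCT400.

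A reader might infer that the plan gives no comparison for ZCT400 at all, or would be blind to a problem there. The documents do not support that. ZCT400 rates are shown beside cylinder-matched controls and beside ZCT300, cylinder enters a logistic model, and SAP 7 names a limit. The table would also reveal a large excess: with 46 subjects at a true 11%, the chance of three or more severe reports is 89%, against 1% at a true 1%. What is missing is narrower, namely a stated limit, an interval for the stratum difference, and a rule for what may be concluded. The regression does not fill this gap. It lists no term for IOL group by cylinder, and at 1% it would have about 264 × 0.01 = 2.6 events.

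The pass rates also depend on assumptions. They fall at a 2% base rate and fall further if ZCT300 carries an excess of its own, but in every scenario tabulated a pass remains more likely than not.

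Finally, one might wish to add a ZCT400 test as a second confirmatory step. There is no quota for high-cylinder controls, and Protocol v3.0 followed an interim analysis of severe-distortion rates in an open-label study, so such a step could not now be called cleanly prespecified. That objection is accepted; the fix keeps the result supportive.

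**Conclusion.** The concern holds in a limited form. The pooled test is sound for the pooled toric group but says little about ZCT400: a score-type test passes about 95% and 83% of the time at ZCT400 excesses of 10 and 14 points with a 1% base rate, and 91% and 76% at 2%. If ZCT300 is itself 2 points above control, the range is about 58% to 83% across both excesses and the interval methods. These figures assume 106, 46 and 112 evaluable subjects and, except in the last case, ZCT300 equal to control.

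Separately, and without any assumption, the SAP justifies the ZCT400 subgroup by an upper limit that none of its listed outputs contains. That justification rests on about 70 subjects, against 51 planned in the current protocol.

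**What to change.** In SAP 4.2, SAP Appendix I and Protocol 20.2, add for the high-cylinder stratum:

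1. the exact one-sided 95% upper limit for the ZCT400 severe-distortion rate;
2. the toric-minus-control difference with a two-sided 90% score interval (Miettinen-Nurminen or Farrington-Manning), shown beside the 0.10 margin and labelled supportive. Name the method outright. A reference to the primary method would not be enough, since none is specified, and Wald is too liberal at this size.

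Restate the SAP 7 precision for about 46 evaluable ZCT400 subjects. Word the primary conclusion as applying to the pooled toric group, and let any statement about ZCT400 rest on items 1 and 2.

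The cost is one table from data and strata already planned; the primary test is unchanged. The downside is that, at true rates of 2% in both groups, there is about a 15% to 19% chance that the ZCT400 interval does not exclude 10 points. That range assumes 11 to 56 high-cylinder controls, a number that the documents do not fix.

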4.2 Other Visual Distortion Endpoints Related to Severe Visual Distortions

In addition to the above information related to the primary endpoint analysis, other analyses will also be performed for severe visual distortion rates (based on the 5 defined items) and will include the frequency and proportion with severe visual distortions. Severe visual distortion data for the overall circumstance will be reported for the low (ZCT300) and high cylinder (ZCT400) subgroups for bilateral subjects to evaluate if there is a trend of increasing severity for the higher cylinder IOL group. The severe visual distortion rate will also be reported by IOL group for all subjects (bilateral plus those implanted in one eye (with a cataract, phakic or having another IOL in the fellow eye). In addition, an analysis including all subjects using imputed data for subjects with no questionnaire data available at any visit will also be reported.

Additional analyses including covariates will also be performed for bilateral subjects. A logistic regression model with overall severe visual distortion rates as the dependent variable and IOL group, age, gender, race, cylinder power (low- vs high-cylinder subgroups) and the interaction of age with IOL group and gender with IOL group as independent variables will be performed to further evaluate the influence of these variables on severe visual distortions. If covariates are shown to be important then additional analyses will be provided for those covariates. Results for severe visual

distortions will also be reported by study site for each IOL group. Although there are a large number of sites, any unusual patterns will be noted (i.e. all severe visual distortions at 1 or 2 sites) and further analyses performed to address any site issues.

To evaluate if IOL axis misalignment changes are associated with severe visual distortions, descriptive statistics for IOL axis misalignment will be reported for Toric subjects with and without severe visual distortions. In this study, axis misalignment is defined as the difference between the Toric IOL axis marker location from the slit lamp evaluation and the steep meridian from the postoperative keratometry measurement. This measurement is intended to evaluate toric IOL misalignment as a possible reason for severe visual distortions experienced by a subject at a specific postoperative timepoint. This axis misalignment measurement is not a measure of toric IOL rotational stability, but a measure of toric IOL alignment relative to post-surgical keratometry steep meridian [as it is known that cataract surgery can induce changes in the cornea].

4.3 Other Visual Distortion Endpoints:

The frequency and proportion with each response will also be reported for individual visual distortion items on the questionnaire and will be reported by IOL group for bilateral subjects for overall and with and without correction.

4.4 Other Safety Endpoints:

The frequency and proportion of medical and lens findings will also be reported for first and second eyes of toric (ZCT) and control (ZCB00) subjects. The frequency and proportion of adverse events at any time postoperative will also be reported.

For subjects with serious or device related adverse events or reports of severe visual distortions, additional detailed information will be provided as appropriate and may include such items as uncorrected and corrected distance visual acuity, manifest refraction, keratometry, intraocular pressure, slit-lamp and dilated fundus exam findings, ocular medications, questionnaire responses and prognosis and treatment.

5. One Month Prescription Data:

The frequency and proportion of responses to the question related to offering of spectacle or contact prescription will be reported by IOL group at the one month visit.

6. One Year Data:

Visual distortion findings, adverse events and medical/lens findings at one year will be reported for subjects who experienced a repositioning procedure during the study and for subjects who were reported with severe visual distortions at the 6-month visit.

7. Sample Size Calculations

With 200 toric (ZCT) subjects and 150 control (ZCB00) subjects, this study has over 90% power to evaluate the rate of severe visual distortions for toric subjects as being no more than 10 percent higher than control subjects. This assumes use of one side of a two-sided 90% confidence interval and severe visual distortion rates of 0.02 for toric and control subjects.

With approximately 70 subjects in the higher cylinder toric subgroup (those with a ZCT400 IOL in one or both eyes) the precision of the one-sided upper confidence limit for the proportion of those with severe visual distortions is approximately 0.05 to 0.06 assuming a rate for severe visual distortions of 0.02.

REFERENCES

- 1. Little, R.and Rubin, D. Statistical Analysis with Missing Data, John Wiley & Sons, Inc. New York, Second Edition, (2002)
- 2. SAS Institute. The MI and MIanalyze Procedures. SAS/STAT 9.2 User Guide. Cary, N.C.

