**Number of subjects:**

A minimum of 396 subjects will be enrolled to achieve bilateral implantation in approximately 294

subjects: 169 TECNIS Toric ZCT300 and ZCT400 subjects (including a minimum of approximately 30%, or 51, ZCT400 subjects) and 125 control subjects (assumes a 10% drop-out rate for a minimum of 152 toric and 112 control subjects available for evaluation at 6 months). Subjects will choose to be implanted with the same lens in both eyes, either the toric IOLs or the non-toric control IOL.

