# Patient Reported Visual Distortions Questionnaire (PRVDQ)

---

This questionnaire asks about the severity of visual distortions **OVER THE LAST 7 DAYS**. If your vision is different between eyes, please respond with how you see with both eyes in general. For each question, please indicate if you have experienced the “visual distortion” under these **3 circumstances**:

- A. When **NOT** wearing corrective glasses (including reading glasses) or contacts
- B. When **WEARING** corrective glasses (including reading glasses) or contacts.
- C. Overall (taking all things into account)

Please read each question carefully and answer as honestly as you can without the help of anyone. There are no right or wrong answers.

For ALL questions, please mark an  in the box that best describes your answer.

**Blurred vision at all distances** may be described as a lack of vision sharpness resulting in the inability to see fine detail.

Q1. Please rate the severity of **blurred vision at all distances** you experienced over the LAST 7 DAYS...

	Did not experience	Mild	Moderate	Severe	Does not Apply
	▼	▼	▼	▼	▼
a. When not wearing corrective glasses or contacts (including reading glasses).....	 0	 1	 2	 3	 4
b. When wearing corrective glasses or contacts (including reading glasses) .....	 0	 1	 2	 3	 4
c. Overall (taking all things into account).....	 0	 1	 2	 3	

**Hazy vision** may be described as looking through fog or smoke.

Q2. Please rate the severity of **hazy vision** you experienced over the LAST 7 DAYS...

	Did not experience	Mild	Moderate	Severe	Does not Apply
	▼	▼	▼	▼	▼
a. When not wearing corrective glasses or contacts (including reading glasses).....	 0	 1	 2	 3	 4
b. When wearing corrective glasses or contacts (including reading glasses) .....	 0	 1	 2	 3	 4

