Statistical Analysis Plan

POST-APPROVAL STUDY OF THE TECNIS® TORIC IOL, MODELS ZCT300 AND ZCT400

NCT Number: NCT02566083

Document date: 24 Jun 2015

STATISTICAL ANALYSIS PLAN

Protocol

TIOL-202-TPAS

POST-APPROVAL STUDY OF THE TECNIS® TORIC IOL, MODELS ZCT300 AND ZCT400

1. Introduction

This document summarizes the statistical methods to be implemented during the analysis of data for the post-approval study of the TECNIS® Toric IOL models ZCT300 and ZCT400. The purpose of this study is to evaluate the rates of severe visual distortions for the TECNIS Toric IOLs with >2.0 D of cylinder correction at the corneal plane in a larger population in clinical practice compared to a control (model ZCB00). This study will be a prospective, multicenter, bilateral, open-label, parallel group clinical investigation. Subjects are to be bilaterally implanted with the toric ZCT (models ZCT300 and ZCT400) or the control ZCB00 IOL.

The key timeframe for analysis will be the six month visit. The primary endpoint for this study is the rate of severe visual distortions defined as the proportion of subjects who report a severe visual distortion under overall circumstances at 6 months for any of the following 5 visual distortion items of interest:

- •lines that slant, tilt, split or separate
- •flat surfaces appearing curved
- •objects appearing further away or closer than they actually are
- •objects appearing to have a different size or shape
- physical discomfort related to vision

For the primary endpoint, severe visual distortions will be assessed using the overall circumstance reply at the 6 month visit. For the primary endpoint, the frequency and proportion of subjects reporting one or more of these items as severe will be used to determine the rate of severe visual distortions.

Results from individual visual distortion items on the PRVDQ questionnaire will also be reported for overall and with and without correction..

Other endpoints include: rates of IOL repositioning procedures (secondary surgical intervention) due to IOL misalignment and rates of other adverse events.

2. Analysis Populations and Data Conventions

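### SAP 4.2 asks whether severity rises in the higher-cylinder group but compares cylinder subgroups only on the yes/no severe rate, leaving the 0–3 grades out of that comparison

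*SAP*

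**What the plan says.** **Question and measure.** SAP 4.2 states: "Severe visual distortion data for the overall circumstance will be reported for the low (ZCT300) and high cylinder (ZCT400) subgroups for bilateral subjects". The stated purpose is "to evaluate if there is a trend of increasing severity for the higher cylinder IOL group". The outcome is the five-item yes/no measure of SAP section 1: "the frequency and proportion of subjects reporting one or more of these items as severe will be used to determine the rate". The logistic model in SAP 4.2 has a term for cylinder subgroup, but its dependent variable is the same yes/no outcome. Protocol 20.2 repeats the binary version without a trend aim: "rate of severe visual distortions will also be presented for those in the low- and high-cylinder subgroups".

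**Grades collected.** Of the PRVDQ, protocol Appendix B says: "This questionnaire asks about the severity of visual distortions". Each overall reply is scored 0 (not experienced), 1 (mild), 2 (moderate) or 3 (severe).

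**Use made of the grades.** SAP 4.3 says: "The frequency and proportion with each response will also be reported for individual visual distortion items on the questionnaire". That table is by IOL group, as in protocol 20.3. Among the distortion rows of SAP Appendix I, only the severe-rate row is marked for cylinder subgroup. The individual-item row is not.

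**Subgroup size.** The protocol synopsis plans 169 toric subjects, "including a minimum of approximately 30%, or 51, ZCT400 subjects". Protocol 20.6 adds: "This assumes severe visual distortion rates of 1% for both the toric and control subjects". SAP section 7, dated 2015, works instead with about 70 higher-cylinder toric subjects and a 2% rate.

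**The concern.** The question is about severity and the measure is a single cut at its top end. A shift from none or mild to moderate in ZCT400 subjects would leave that measure unchanged. Because severe reports are expected to be rare, the subgroup table may well show no or one severe subject per cell. A table of that kind is easily read as showing no trend, when it had little chance of showing one. Grades that could show a shift are collected on every subject who completes the questionnaire, but no planned output sets them against cylinder power.

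**Working it through.** **1. The plan's own figure.** SAP section 7 gives a one-sided upper limit of about 0.05 to 0.06 for n = 70 and rate 0.02.
- Wald, one-sided 95%: 0.02 + 1.645 × √(0.02 × 0.98 / 70) = 0.0475.
- With 1.96 in place of 1.645: 0.053.
- Exact limit with 1 of 70: 0.066.

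The stated range lies among these, so it is reproduced. It describes one group's rate, not a comparison of cylinder groups.

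**2. Severe subjects expected in the higher-cylinder toric group.** Expected count = n·p; chance of none = (1 − p)^n; one-sided 95% upper limit after zero events = 1 − 0.05^(1/n).

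| Basis | n | p | Expected | Chance of none | Upper limit if none |
|---|---|---|---|---|---|
| Protocol v3.0 (51 × 0.9 = 45.9) | 46 | 1% | 0.46 | 63% | 6.3% |
| Protocol n, SAP rate | 46 | 2% | 0.92 | 39% | 6.3% |
| SAP section 7 | 70 | 2% | 1.4 | 24% | 4.2% |

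**3. High against low cylinder on the severe rate.** Low-cylinder toric sizes are by subtraction: 152 − 46 = 106 (protocol) and 200 − 70 = 130 (SAP). Power of a one-sided 0.05 Fisher exact test:

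| Sizes, low-group rate | Doubling | Tripling | Five-fold |
|---|---|---|---|
| 46 v 106, 1% | 3% | 8% | 23% |
| 70 v 130, 2% | 10% | 27% | 69% |

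With 46 v 106 and no severe ZCT300 subject, three severe ZCT400 subjects are needed for p < 0.05 (2 v 0 gives p = 0.090; 3 v 0 gives 0.026).

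**4. What the grades could add (illustration).** The documents give no distribution of grades, so the low-group shares below are assumptions, as are proportional odds and the odds ratios. Example: shares of none/mild/moderate/severe of 70/22/7/1% and odds ratio 3.
- Severe: odds 0.01/0.99 × 3 = 0.0303, which is 2.9%.
- Moderate or severe: odds 0.08/0.92 × 3 = 0.261, which is 20.7%, up from 8%.
- Any grade above none: odds 0.30/0.70 × 3 = 1.286, which is 56.3%, up from 30%.

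The same test is applied to both outcomes: z = (mean score high − mean score low) / √(V × (1/46 + 1/106)), where V is the pooled score variance, rejecting when z > 1.645. The score is 0/1 for severe yes/no and 0–3 for the grade. Simulated power:

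| Assumed low-group shares | Grade, OR 2 | Grade, OR 3 |
|---|---|---|
| 95/3/1/1% | 27% | 52% |
| 90/7/2/1% | 37–38% | 71% |
| 85/11/3/1% | 46% | 81% |
| 70/22/7/1% | 60% | 92–93% |

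For severe yes/no the power is about 10–11% at OR 2 and 20–21% at OR 3 for every row, because the severe share is 1% throughout. At OR 1 in a run of 100,000 replicates, the test rejects in about 5–6% of cases for the grade and about 3% for severe yes/no. A small part of the gap is therefore a difference in size.

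**The case against.** Several stronger readings are tempting and do not hold.

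- **That the grades are discarded.** They are not. SAP 4.3 and protocol 20.3 tabulate every response to every item, toric against control. What is missing is the split by cylinder subgroup and a per-subject summary.
- **That no severe event is the likeliest result in the ZCT400 group.** This depends on the inputs. It is so under protocol v3.0 (63%), where 51 is a minimum. Under SAP section 7 the chance is 24%.
- **That the question cannot be answered.** A very large difference could be seen: power for a five-fold rise is 23% to 69%. SAP section 7 frames the subgroup as estimation, and even 0 of 46 bounds the rate at 6.3%. No document promises a powered trend test. That stands, but a bound on one group's rate does not speak to a trend.
- **That the study is confined to these models in order to compare ZCT300 with ZCT400.** The background concerns toric lenses with higher correction as a class, and the hypothesis compares them with a non-toric control. The cylinder contrast (2.06 v 2.74 D at the corneal plane) is secondary.
- **That grades raise power from 7% to 93%.** That contrast sets a conservative Fisher test against a score test at the most favourable assumptions. With the same test the gain is real but smaller.

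It can also be argued that SAP 4.2 merely uses loose words for a higher severe rate. Rewording would then remove the mismatch, but not the weakness of the comparison in step 3.

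Two cautions on the remedy stand. High-cylinder subjects also have more corneal astigmatism, so a toric-only comparison cannot separate lens from cornea. And a worst-of-five grade lets physical discomfort count equally with tilted lines.

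**Conclusion.** The point holds as a mismatch between the question in SAP 4.2 and the measure used to answer it. No planned table or model shows the 0–3 grades by cylinder subgroup, and the severe rate alone would usually miss a doubling or tripling (power 3–27% by Fisher across both sets of inputs).

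The event counts rest on the documents' own sizes and rates. The low-cylinder sizes come from subtraction. The ordinal power figures (27–60% at OR 2, 52–93% at OR 3) rest on assumed grade distributions and proportional odds, and only illustrate the direction and rough size of the gain.

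The primary endpoint and its non-inferiority test are unaffected. The change is worth making because it serves the SAP's own question with data already collected.

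**What to change.** Keep the primary endpoint. Before the final analysis, add to SAP 4.2 and Appendix I, labelled exploratory:

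1. A table of each bilateral subject's worst overall grade (0–3) across the five items, by low and high cylinder subgroup within both toric and control, using the control classification already in SAP 2.1.
2. The moderate-or-severe rate in each of those four cells, with its confidence interval.
3. An ordinal comparison of high with low cylinder (mean-score or proportional-odds). Show the control subgroups alongside, or include an IOL group by cylinder term, so that a lens effect is not confused with higher corneal astigmatism.
4. A sentence saying that a low severe rate in the higher-cylinder subgroup is not evidence of no trend.

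The cost is SAP wording and one more exploratory analysis from existing data, with no change to visits, subjects or the primary test. That analysis may itself have limited power, particularly for an interaction term or if most subjects report no distortion.
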